Evaluation of the first 6 patients in each treatment arm will occur after all patients have completed two cycles of treatment (or at least 56 days from the first day of treatment). Enrollment will be halted while the first 6 patients in each treatment arm are evaluated for safety. The treatment combination will be considered as safe, and continue to enroll to a total of 21 patients (Arms E-F) or 24 patients (Arms C-D) or 30 patients (Arm B) when there are no more than 1 out of 6 patients with DLTs in the first cycle of treatment. If any patients in the first 6 of each treatment arm withdraw from the study without a DLT event prior to completing the first cycle of treatment, they will be replaced for the assessment of DLT rate. This will allow for early identification of significant toxicities and early stoppage in potentially toxic arms. If 2 or more out of 6 patients have DLTs in the first cycle of treatment in any arm, then an additional 6 patients will enroll at a next lower dose level to be determined by the PI, sponsor (MDACC IND office), and Pfizer team after reviewing the safety, efficacy, and PD data from the first 6 patients enrolled. If no more than 1 out of the additional 6 patients treated with the lower dose level experience DLTs, this treatment combination will be considered as safe and continue to enroll to a total of 21 patients (Arms E-F) or 24 patients (Arms C-D) or 30 patients (Arm B). If 2 or more out of these 6 additional patients experienced DLTs, then this arm will be halted.

The Investigator is responsible for completing the cohort summary template and submitting to the IND office Medical Monitor for review and approval prior to continuing accrual beyond each set of 6 patients in each arm of the study. A copy of the cohort summary should be placed in the Investigator's Regulatory Binder under "sponsor correspondence". This should be submitted after the first six patients.

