3.5 Cohort enrollment schema

(A) Arms B-E (Azactidine + venetoclax + GO; azacitidine + avelumab + GO; azacitidine + venetoclax + avelumab; azacitidine + avelumab + PF-04518600)

Arms B-E will commence enrollment in parallel with the OX40 arm (namely Arm A). If multiple are open to enrollment the patient allocation will generally follow a rotating sequence between arms unless the PI (or Co-PI) decide to allot a patient to a particular arm. There will be no separate escalation/dose finding cohorts for

these combination arms, but predefined toxicity stopping rules have been built in to monitor for grade 3/4 drug-related toxicities and to stop or de-escalate dose if >30% grade 3/4 drug-related toxicity is observed in any of the combination arms at any given time as outlined in section 3.3 (DLT monitoring in each arm).

(B) Arm F (GO + Glasdegib)

Arm F is the combination of GO + glasdegib. This arm will commence enrollment in parallel with the OX40 arm (namely Arm A). There will be no separate escalation/dose finding cohorts these combination arms but we have built in predefined toxicity stopping rules to monitor for grade 3/4 drug-related toxicities and to stop or de-escalate dose if >30% grade 3/4 drug-related toxicity is observed in any of the combination arms at any given time as outlined in section 3.0 (DLT monitoring in each arm).

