5.2 Schedule

The Investigator is responsible for completing Safety/Efficacy Monitoring summary reports and submitting to the IND office Medical Affairs and Safety Group for review and approval. These should be submitted as follows:

- Arm A:
Every 4 evaluable subjects, after completion of 28 days of study treatment. Study enrollment of this arm must be held until IND approval is obtained.
- Lead-In and Phase II for Arms B to F:
 - Safety monitoring
 - Lead-in: After the first 6 evaluable subjects, per arm, complete 2 cycles of therapy and every 3 evaluable subjects, per arm, thereafter. Enrollment must be halted for that individual arm while the first 6 patients of that arm are evaluated for safety (i.e. after all patients have received 2 cycles of therapy, or been followed for at least 56 days from the start of treatment or at least 56 days from the first dose of venetoclax in the venetoclax containing arms B and D).
 - Phase II: After the first 6 evaluable subjects, per arm, complete 2 cycles of therapy and every 3 evaluable subjects, per arm, thereafter.
 - Futility monitoring
 - Futility summary will be submitted after the first 10 evaluable subjects, per arm, complete 3 cycles of therapy and every 5 evaluable subjects, per arm, thereafter.

The dosing calculations should be based on the body weight. All doses should be rounded to the nearest milligram for all agents. There will be no dose reductions (only interruptions when indicated) allowed for avelumab and PF-04518600 on this trial.

Patients will be treated according to the following schedules that are specific to each arm:

(A) Arm A (PF-04518600 alone in RR AML) (6 patient dose-finding cohort):

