True response rate	Prob(stop the arm early)	Average sample size
0.15	0.878	11.3
0.25	0.585	13.6
0.30	0.428	14.8
0.35	0.291	15.8
0.45	0.108	17.2
0.55	0.029	17.8
0.65	0.005	18.0

Arm E-F

The stopping boundaries for efficacy based on the same assumptions and monitoring conditions are provided in Table 18. The operating characteristics are summarized in Table 19. If the study arm is not stopped early and 15 patients have been treated and evaluated in the study arm, assuming 5 of the 15 patients achieve CRc under the combination treatment, then the 95% credible interval for CRc rate will be (0.13, 0.56).

Arm F will be closed at this time to further enrollment due to lack of clinical efficacy and competing options of higher priority at our institution.

Table 18. Stopping boundaries for futility monitoring in Arm E-F

# of patients evaluated for response	Stop the arm if # of patients with response is less than or equal to:
10	0-2
15	Always stop with this many patients

Table 19. Operating characteristics for futility monitoring in Arm E-F

True response rate	Prob(stop the arm early)	Average sample size
0.15	0.820	10.9
0.25	0.526	12.4
0.30	0.383	13.1
0.35	0.262	13.7
0.45	0.100	14.5
0.55	0.027	14.9
0.65	0.005	15.0

Toxicity Monitoring for Arm B-F

The method of Thall, Simon and Estey will be used for toxicity monitoring for this study. Denote the probability of DLT by P_T . We assume as a priori, $P_T \sim \text{beta}(0.3, 1.7)$. Our stopping rule is: if 2 or more out of 6 patients with DLTs in the first cycle of treatment, then additional 6 patients will enroll at a lower dose level. If 2 or more out of these 6 additional patients experienced DLTs, then this arm will be halted. Otherwise, we will stop the arm if $\Pr(P_T > 0.15 | \text{data}) > 0.80$. That is, we will stop the arm for new patient enrollment if at any time during the study, we determine that there is more than 80%

chance that the toxicity rate is more than 15%. Again, the design parameters are set the same for arms B-F, while separate toxicity monitoring analyses were conducted to accommodate different numbers of patients among these arms.

Arm F will be closed at this time to further enrollment due to lack of clinical efficacy and competing options of higher priority at our institution.

Arm B

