The toxicity stopping rule will be applied starting from the 6th patient, and then in cohort size of 3. Stopping boundaries corresponding to the above stopping rule are listed in Table 18. The operating characteristics are summarized in Table 19.

Table 18. Early stopping boundaries for toxicity monitoring arm B

# of patients (in cohort size of 3, starting from the 6 th patient)	Stop the arm if there are this many patients with toxicities:
6	2-6
9	3-9
12	4-12
15	4-15
18	5-18
21	5-21
24	Always stop

Table 19. Operating characteristics for toxicity monitoring arm B

True toxicity rate	Prob(stop the arm early)	Average sample size
0.10	0.163	21.4
0.15	0.342	19.0
0.20	0.555	16.0
0.25	0.731	13.4
0.30	0.856	11.0
0.40	0.976	8.0

Arm C-D

The toxicity stopping rule will be applied starting from the 6th patient, and then in cohort size of 3. Stopping boundaries corresponding to the above stopping rule are listed in Table 18. The operating characteristics are summarized in Table 19.

Table 20. Early stopping boundaries for toxicity monitoring arm C-D

# of patients (in cohort size of 3, starting from the 6 th patient)	Stop the arm if there are this many patients with toxicities:
6	2-6
9	3-9
12	4-12

15	4-15
18	Always stop

Table 21. Operating characteristics for toxicity monitoring arm C-D

True toxicity rate	Prob(stop the arm early)	Average sample size
0.10	0.137	16.5
0.15	0.290	15.0
0.20	0.485	13.1
0.25	0.653	11.4
0.30	0.771	10.1
0.40	0.936	7.8

Arm E - F

The toxicity stopping rule will be applied starting from the 6th patient, and then in cohort size of 3. Stopping boundaries corresponding to the above stopping rule are listed in Table 22. The operating characteristics are summarized in Table 23.

Arm F will be closed at this time to further enrollment due to lack of clinical efficacy and competing options of higher priority at our institution.

Table 22. Early stopping boundaries for toxicity monitoring arm E-F

# of patients (in cohort size of 3, starting from the 6 th patient)	Stop the arm if there are this many patients with toxicities:
6	2-6
9	3-9
12	4-12
15	Always stop

Table 23. Operating characteristics for toxicity monitoring arm E-F

True toxicity rate	Prob(stop the arm early)	Average sample size
0.10	0.122	13.9
0.15	0.264	12.8
0.20	0.410	11.6
0.25	0.562	10.3
0.30	0.685	9.3
0.40	0.874	7.6

Statistical Analysis Plan

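### The toxicity rules conflict on when they act: fixed looks at patient 6 and every 3 after, or continuously; under the fixed looks a lead-in that has already failed can fill to six

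*Combined protocol and SAP*

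**What the plan says.** Five places bear on when toxicity can stop or hold an arm.

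- **Section 11.0, arm-specific toxicity paragraphs.** "The toxicity stopping rule will be applied starting from the 6th patient, and then in cohort size of 3". The boundary tables (the second Table 18 for Arm B, Table 20 for Arms C-D, Table 22 for Arms E-F) have rows at 6, 9, 12 and so on, and none between.
- **Section 11.0, general toxicity paragraph.** The DLT probability has a Beta(0.3, 1.7) prior. Two or more DLTs in the first six lead to six more patients at a lower dose level, and two or more among those halt the arm. Otherwise the arm stops when the posterior probability that the DLT rate exceeds 0.15 is above 0.80. The explanation that follows reads "we will stop the arm for new patient enrollment if at any time during the study" that condition is met.
- **Section 3.3.** "Evaluation of the first 6 patients in each treatment arm will occur after all patients have completed two cycles of treatment", or 56 days, with enrolment halted during that evaluation. At most one DLT in six counts as safe. A cohort summary must be approved "prior to continuing accrual beyond each set of 6 patients in each arm of the study", although the same paragraph then asks for it after the first six.
- **Section 5.2.** The hold is for the first six patients of an arm. Reports then follow this schedule: "Phase II: After the first 6 evaluable subjects, per arm, complete 2 cycles of therapy and every 3 evaluable subjects, per arm, thereafter".
- **Section 3.5.** For the combination arms, rules are said to be built in "to stop or de-escalate dose if >30% grade 3/4 drug-related toxicity is observed in any of the combination arms at any given time". The sentence refers the reader to Section 3.3, which contains only the six-patient rule.

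**The concern.** The text gives two incompatible answers to a practical question: if two of the first four patients have had a DLT, may the fifth be enrolled? The look schedule, the tables and the hold in Sections 3.3 and 5.2 contain nothing that prevents it, although two or more out of six is by then certain. The general paragraph of Section 11.0 and Section 3.5, read as written, would already have acted.

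Section 3.5 states that the combination arms have no separate dose-finding cohorts, so the lead-in is the first safety test of each triplet in this trial. The reading that staff adopt decides how many patients start a combination that has already failed its own criterion. It also decides whether the published operating characteristics describe the rule actually run.

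**Working it through.** **Inputs (Section 11.0).** Prior Beta(0.3, 1.7); threshold Pr(P_T > 0.15 | data) > 0.80; looks at 6, 9, 12, ...; tabled maxima 24 (Arm B), 18 (Arms C-D) and 15 (Arms E-F). The documents give no accrual rate and no DLT onset times.

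**1. Boundaries.** With x DLTs in n patients the posterior is Beta(0.3 + x, 1.7 + n - x). The smallest x with 1 - F(0.15) > 0.80, where F is the posterior distribution function, is 2 at n = 6 (0.801), 3 at 9 (0.873), 4 at 12 (0.916), 4 at 15 (0.839), 5 at 18 (0.890) and 5 at 21 (0.820). These match the tables.

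**2. Operating characteristics.** An exact binomial recursion with stops only at those looks gives:

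| Arm, true rate | Stated P(stop) / average n | Recomputed |
|---|---|---|
| B, 0.10 | 0.163 / 21.4 | 0.156 / 21.6 |
| B, 0.30 | 0.856 / 11.0 | 0.864 / 10.9 |
| B, 0.40 | 0.976 / 8.0 | 0.976 / 8.0 |
| C-D, 0.30 | 0.771 / 10.1 | 0.781 / 9.9 |
| C-D, 0.40 | 0.936 / 7.8 | 0.937 / 7.8 |

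All 18 stated stop probabilities for Arms B-F agree within 0.02 (largest gap 0.012). The tables therefore assume fixed looks.

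**3. Fixed looks: a lead-in that has already failed.** For k patients, P(at least 2 DLTs) = 1 - (1-p)^k - k p (1-p)^(k-1).

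| True rate p | k=2 | k=3 | k=4 | k=5 | k=6 |
|---|---|---|---|---|---|
| 0.15 | 0.022 | 0.061 | 0.110 | 0.165 | 0.224 |
| 0.30 | 0.090 | 0.216 | 0.348 | 0.472 | 0.580 |
| 0.40 | 0.160 | 0.352 | 0.525 | 0.663 | 0.767 |

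Patient k+1 enters after the second DLT if two DLTs have occurred among the first k. The expected number entering after it within the six is therefore the sum over k = 2 to 5:

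- p = 0.30: 0.090 + 0.216 + 0.348 + 0.472 = 1.13
- p = 0.40: 0.160 + 0.352 + 0.525 + 0.663 = 1.70
- p = 0.15: 0.36

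This assumes that each DLT is known before the next patient enters. Section 3.4 sets a 28-day window, 42 days for neutropenia, and longer when venetoclax starts late, so these are upper bounds. After the lead-in, the overrun between looks is at most 1-2 patients and averages about 0.03-0.2 per arm.

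**4. Literal continuous reading.** The posterior for two DLTs in 2, 3, 4, 5 and 6 patients is 0.971, 0.939, 0.898, 0.852 and 0.801, so every case in step 3 would already stop. But 1/1 (0.849), 3/10 (0.838) and 3/11 (0.801) would stop too. A stop at 1/1 contradicts the rule that one DLT in six is safe. Stops at 3/10 and 3/11 contradict the tables, where three DLTs at patient 9 stop the arm and otherwise four are needed at patient 12. Applying the criterion after every patient gives an Arm B stop probability of 0.224 at a 10% rate, against 0.163 stated.

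**5. Section 3.5.** Two events in six patients is 33%, above 30%. So is one event in three (33%), two (50%) or one (100%). The events counted are grade 3/4 drug-related toxicities, which need not be DLTs, and no minimum number of patients is given.

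**6. Pausing at the existing boundaries.** If enrolment stops as soon as the count reaches the next look's boundary, every stop decision is the same, so the stop probabilities do not move. Average sample size falls as follows:

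| Arm | Rate 0.30 | Rate 0.40 |
|---|---|---|
| B | 10.9 to 9.6 | 8.0 to 6.1 |
| C-D | 9.9 to 8.7 | 7.8 to 6.0 |

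The savings are upper bounds for the reason given in step 3. Like the tables, they treat 2/6 as a final stop and ignore the lower-dose cohort.

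**The case against.** A reader might infer that no toxicity trigger acts before the sixth patient or between looks. The documents do not support that. The general paragraph of Section 11.0 and Section 3.5 both state numeric triggers not tied to a group of patients, and taken literally the first stops every lead-in case described. Section 9.2 also lets the principal investigator and the IND office suspend enrolment at their discretion, and serious adverse events reach the IND office within 5 working days (Section 10.3) and the manufacturer within 24 hours (Section 10.5). Neither has to wait for patient 6.

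That answers the absolute claim but not the conflict. The continuous wording contradicts the tables and the one-in-six rule. The futility text uses similar wording and then sets fixed looks, which suggests a loose gloss on scheduled looks. Section 3.5 counts a different event and refers to a section that lacks its threshold. Discretion under Section 9.2 is not a numeric rule.

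Three further objections stand in part. The exposure is modest: 0.36 patients per lead-in at a 15% rate, even as an upper bound. The 56-day review does not itself prolong enrolment, because accrual is halted during it. The wording about each set of six in Section 3.3 may simply mean the first six and the lower-dose six, so its mismatch with Section 5.2 is the weakest part of the point.

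**Conclusion.** The point holds as a conflict among stated safety rules that changes what the trial would do. The stated operating characteristics belong to the fixed-look reading, which lets an arm fill to six after the lead-in criterion has been met. That situation arises by patient 5 in 47% of lead-ins at a true DLT rate of 30% and 66% at 40%, with at most about 1.1 and 1.7 further patients enrolled on average. The effect between later looks is minor. The literal continuous reading removes this overrun but is a different design, with more false stopping than the tables state.

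The lead-in probabilities assume independent patients with a common DLT rate. The Arm B and Arms C-D figures take patient numbers as the tables count them. The tabled maxima (24, 18, 15) are each six below the planned totals in Section 3.3 (30, 24, 21), so whether the lead-in six are counted needs separate clarification.

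**What to change.** Reconcile Sections 3.3, 3.5, 5.2 and both toxicity passages of Section 11.0 so that one rule governs. The text should state:

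1. whether the posterior criterion applies only at the tabled looks or after every patient, with operating characteristics to match;
2. whether enrolment pauses once an existing tabled boundary is certain to be crossed, including before the sixth patient;
3. whether DLT counts restart in the lower-dose cohort of six;
4. how the 30% trigger in Section 3.5 relates to the DLT rule, and which section defines it;
5. after which patients the cohort summary must be approved before accrual continues.

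Which clinical rule applies is for the sponsor to decide. Statistically, pausing at the sponsor's own boundaries leaves the tabled stop probabilities as they are and lowers the average sample size. The cost is protocol wording. The small downside is that fewer patients' data would be available when the lower dose level is chosen, because Section 3.3 bases that choice on the first six. If the continuous reading is kept, the toxicity tables must be recalculated and the one-in-six rule reconciled with it.

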12.0 PROTOCOL ADMINISTRATION

This study will be monitored by the MD Anderson IND Office and a protocol-specific monitoring plan will be followed.

Protocol amendments

Changes to the protocol will be made only when protocol amendments have been signed by the principal investigator and approved by Pfizer and the IRB of the study center.

Archival of data

MD Anderson-IND study must retain all records *indefinitely*.

